10.1.12 Pregnancy Reporting

This process is aimed at ensuring the appropriate monitoring of the potential risk related to IMP exposure of pregnant women and/or foetuses as well as the risks associated with exposure of a father, regarding congenital abnormalities or birth defects in their offspring. It also ensures compliance with applicable international and local regulations.

The requirements are applicable to all subjects following exposure to IMP.

Female trial subjects: The trial subject must be advised by the investigator to inform him/her immediately if she suspects she may be pregnant believes that conception occurred within 30 days after IMP administration.

Male trial subjects: The trial subject must be advised by the investigator to inform him/her immediately if he suspects his partner became pregnant within 30 days after IMP administration.

When a trial subject reports a pregnancy (post-IMP administration) to the investigator, a pregnancy test should be arranged for the trial subject (or their partner) by the investigator within 7 days of the pregnancy being reported.

The investigator must inform the sponsor/CRO within 24 hours of receiving positive pregnancy test results using a copy of the relevant CRF page (demography or AE). The investigator should include an estimated date of conception when communicating with the sponsor/CRO, as follow-up after end of pregnancy is required.

A reported pregnancy will be followed to determine the outcome. The investigator will collect follow-up information on the participant and the neonate and the information will be forwarded to the sponsor. Generally, follow-up will not be required for longer than 6 to 8 weeks beyond

the estimated delivery date. Any termination of pregnancy will be reported, regardless of foetal status (presence or absence of anomalies) or indication for the procedure.

10.2 Secondary Outcome Measures

Dosimetry estimates and cumulated activity by source region and by entire body (including whole blood, plasma, and excreted urine) at time points up to 48 hours after administration in HVs.

10.2.1 Biodistribution

One of the secondary objectives of this study is to determine the biodistribution of ioflupane (^{123}I) injection after IV administration to Chinese HVs. Biodistribution data in HVs will consist of ^{123}I activity in organs and tissues of interest at multiple time points, ^{123}I activity in whole blood and plasma at multiple time points, and ^{123}I activity in voided urine. The ^{123}I activity in voided urine will be calculated as the product of the ^{123}I activity measured in each void multiplied by the volume of that void. The absorbed doses of radiation to organs and tissues will be evaluated for the Cristy-Eckerman female and hermaphrodite male phantoms [Cristy and Eckerman 1987]. Descriptive statistics of absorbed doses to the target organs and tissues specified in the MIRD schema will be tabulated.

Evaluation of radiation dosimetry outcome measures includes assessing the counts in ROIs from whole-body images, and the assay of radioactivity in whole blood, plasma, and urine.

This will enable the following:

- Estimation of whole-body retention of ^{123}I at each imaging time point post-injection
- Estimation of individual organ uptake, washout and retention of ^{123}I at each imaging time point post-injection
- Estimated clearance of administered ^{123}I in whole blood and plasma
- Estimation of elimination of ^{123}I in blood and urine
- Calculation of the absorbed radiation dose in target organs and tissues
- Calculation of ED

10.2.1.1 Image Acquisition

Whenever possible, images will be acquired at prespecified time points and without any interference in appropriate medical care; the latter will take priority. The sponsor will provide a detailed Imaging Manual to the site which contains a full description of planar and SPECT imaging procedures.

10.2.1.2 Radioactive Counts in Region of Interest and Biodistribution Measurements

In HVs, quantitative measurements of ^{123}I activity in ROIs (including, but not limited to, lungs, heart, liver, gallbladder, spleen, kidneys, gastrointestinal tract and urinary bladder) will be made at several time points post-injection. Time-activity curves will be generated and integrated to obtain the cumulated activity in each region, and these values will be used to determine the internal radiation dosimetry by using the MIRD schema [Siegal et al 1999].

The temporal variations of ^{123}I activity concentrations in whole blood and plasma and the rate and amount of ^{123}I activity excreted through the urinary pathway will be measured.

10.2.1.3 Counting of ^{123}I in Blood, Plasma, and Urine

Ioflupane ^{123}I activity in whole blood, plasma, and urine will be measured by using a gamma counter according to the working instructions at the site. Sample volumes will be adjusted to avoid counter saturation. For time points of blood and urine sampling, see [Table 1](#). A full description of blood and urine collection procedures will be given in Imaging Manual.

(a) Whole Blood and Plasma Assays

For HVs, up to 5 mL venous blood samples will be taken at multiple time points to allow measurement of ^{123}I content in whole blood and plasma over time.

The maximum amount of blood taken for activity counting will be 55 mL for HVs.

The up to 5 mL sample is withdrawn from the subject to a labelled collection tube, and the time of sampling is noted. The times at which samples will be assayed after collection will be specified in the Imaging Manual provided by the sponsor. The time at which the blood sample is taken and the time at which the ^{123}I counting is started will be recorded in the radioactivity counting system, as will be the number of counts per specified time interval. The beginning of injection will be considered time zero.

Following removal of an aliquot of blood for whole-blood activity counting, the remaining blood will be centrifuged to obtain plasma. Immediately thereafter, an aliquot of the resulting supernatant (i.e., plasma) will be transferred with a fresh disposable pipette to a pre-labelled tube for activity counting. The time at which the blood sample is taken and the time of ^{123}I counting will be recorded in the CRF, as will be the number of counts per specified time interval in 0.5 mL plasma. The beginning of injection will be considered time zero.

(b) Urine Assays

Subjects will be asked to void from approximately 1 hour before IMP administration. Urine will be collected whenever voided up to a period of 48 hours post-administration. The total volume of the sample and the time of collection will be accurately recorded in the CRF.

Radioactivity in each urine sample should be recorded in the CRF together with the volume measured, the total urine volume, and the time of measurement. The beginning of injection will be considered time zero.

10.2.2 Assessment of Striatal Binding Ratio

Left and right striatal binding ratios (SBR) will be determined from brain SPECT images acquired at 3 and 6 hours after administration.

10.2.3 Standard of Truth, Comparator, or Reference Imaging

No standard of truth, comparator, or reference imaging will be used in this study.

10.2.4 Image Interpretation and Correlation with Standard of Truth

Images obtained will be analysed by using ROIs in order to quantify counts in the organs of interest at prespecified time points. There will be no standard of truth in this trial as it is not a trial to assess diagnostic efficacy.

10.2.5 Radiation Dosimetry

The calculation of radiation dosimetry will be done in accordance with the sponsor's SOP for radiation dosimetry studies, unless otherwise specified. For HV data, the absorbed doses per unit administered activity to organs and tissues will be estimated using the cumulated activities [\[Stabin et al 2005\]](#). The ED per unit administered activity will be evaluated from this ensemble of absorbed dose data. A summary of the biodistribution and radiation dosimetry data will be presented in the clinical study report, and a full report produced by the sponsor.

10.2.6 Effective Dose

A secondary objective of this study is to determine the ED of ioflupane (^{123}I) injection after IV administration to Chinese HVs. The cumulative activities will be used to calculate the absorbed doses to organs and tissues per unit of administered activity [\[Stabin et al 2005\]](#). The ED per unit of administered activity will be evaluated from this ensemble of absorbed dose data.

10.3 Other Variables

Demographic data (age/date of birth, weight, height, BMI, sex and race) will be collected during the screening visit. Data on the subject's medical and surgical history will be collected at the screening visit. Data on the subject's concomitant medications will be collected from the screening visit to follow-up visit.

11 DATA HANDLING AND QUALITY ASSURANCE

11.1 Completing and Signing Case Report Forms

For electronic CRFs, data will be entered by trained site personnel. Any errors should be corrected within the electronic system. The audit trail will record all changes made, the date and time of the correction, and the person correcting the error. The appropriate electronic signature will be provided.

11.2 Clinical Data Management

The sponsor or CRO will be responsible for the processing and quality control of the data. Data management will be carried out by the sponsor or CRO. The handling of data, including data quality control, will comply with all applicable regulatory guidelines.

11.3 Archiving

All study documentation at the investigator site and sponsor site will be archived in accordance with ICH E6-GCP and the sponsor/CRO's quality standards and SOPs.

12 STATISTICAL METHODS AND PLANNED ANALYSIS

The data will be analysed by the sponsor and/or designated CRO. Any data analysis carried out independently by the investigator should be submitted to the sponsor before publication or presentation.

The data will be summarised with respect to demographic and baseline characteristics, safety observations and measurements, biodistribution, and radiation dosimetry.

12.1 General Statistical Considerations

Tabulations of summary statistics, graphical presentations, and statistical analyses will be performed with SAS® software, Version 9.2 or higher. Descriptive statistics for continuous data in summary tables will include the number of subjects in the analysis (n), mean, standard deviation, median, and range (minimum, maximum). Descriptive statistics for categorical data in summary tables will include counts and percentages. The last observation prior to administration of IMP will be used as the baseline value for calculating changes from baseline after administration of IMP. All data obtained on the CRF and entered into the database will be provided in separate data listings showing individual subject values. The planning and reporting of statistical analysis will be carried out as described in the sponsor/CRO's SOPs governing clinical studies.

12.2 Populations for Analysis

All subjects who receive ioflupane (¹²³I) injection will be included in the safety analysis set.

Subjects who receive ioflupane (¹²³I) injection, undergo planar scintigraphy, have a complete set of images and complete blood sampling at prespecified timepoints will be included in the pharmacokinetic analysis set. Subjects who do not meet all of these criteria may be replaced.

12.3 Subject Demographics/Other Baseline Characteristics

A table will be provided with the following information:

- Number of subjects enrolled.
- Number of subjects included in the safety analysis.
- Number of subjects included in the pharmacokinetic analysis.
- Number of subjects withdrawn from the study and the reason for withdrawal.

Demographic information: Age, height, weight, and BMI will be summarised by using descriptive statistics. Sex and race will be summarised by counts and percentages.

Medical history will be summarised by counts and percentages.

12.4 Study Treatments

IMP information, including the duration of the injection, saline flush volume, radioactivity and volume in syringe prior to administration, and total radioactivity administered, will be summarised.

Any concomitant medication, including indication, given to a subject from 14 days prior to IMP administration throughout the follow-up visit at 2 weeks (\pm 2 days) after IMP administration, will be tabulated by counts and percentages using the World Health Organisation Drug Directory (WHO Drug), Version June 1, 2015 or later, and summarised by Anatomic Therapeutic Chemical Code Level 3 and preferred name.

12.5 Primary Analysis (Safety)

All safety data will be listed by subject number and time point (if applicable). No confirmatory hypothesis testing is intended to be performed. *P*-values will be interpreted as a metric of uncertainty. All data will be listed by subject number and time point (if applicable). Confidence intervals, both individual and simultaneous, will be at the 95% confidence level unless otherwise noted. The last pre-administration observation will be used as the baseline value for calculating post-administration changes from baseline.

An overall summary of AEs will be presented, and they will be coded with Medical Dictionary for Regulatory Activities (MedDRA) and summarised by MedDRA system organ class and preferred term.

Observations and changes from baseline in the results of the physical examination, vital signs and oxygen saturation, 12-lead ECG, and clinical laboratory evaluation (haematology, serum biochemistry, and urinalysis) will be summarised (see [Table 1](#)). Other safety measures that will be summarised including results of tolerability questionnaire and injection site monitoring, and concomitant medications.

12.5.1 Clinical Laboratory Evaluation

Descriptive statistics will be displayed for the observed values and changes from baseline. In addition, for each clinical laboratory variable and each time point, the following safety outcome measures will be summarised by counts and percentages:

- The occurrence of 1 or more changes from baseline, at each post-administration time point, greater than 40% and 80% of the span of the normal limits (not applicable to qualitative parameters).
- The occurrence of post-administration values outside the normal limits (not applicable to qualitative parameters). Shift tables based on the normal range will be prepared.

12.5.2 Vital Signs and Oxygen Saturation

Descriptive statistics will be displayed for the observed values and changes from baseline. For each vital sign and oxygen saturation variable and each time point, the following safety outcome measures will be summarised by counts and percentages:

- The occurrence of 1 or more changes from baseline, at each post-administration time point, greater than a pre-specified magnitude (20 mm Hg for systolic blood pressure, 10 mm Hg for diastolic blood pressure, 10 beats/min for heart rate, 1.5°C for body temperature, 10 breaths/min for respiration rate, and 5% for oxygen saturation).
- The occurrence of post-administration values outside the normal limits (Section 15.3). Shift tables based on the normal range will be prepared.

12.5.4 Physical Examination

The number and percentage of subjects with changes in physical examination status from normal at baseline to abnormal at each post-administration time point (and vice versa) will be presented. Shift tables based on the normal range will be prepared.

12.5.5 Adverse Events

The number and percentage of subjects with 1 or more AEs will be summarised. Summaries will also be presented by AE intensity and judged relationship to IMP.

SAEs will be presented separately. TEAE will be presented separately.

Other significant AEs, will also be summarised.

12.5.6 Tolerability Questionnaire

The results of the tolerability questionnaire performed pre- and post-injection will be summarised. The boxplot of values over time will be plotted for each tolerability parameter.

12.5.7 Injection Site Monitoring

The findings of injection site monitoring pre- and post-injection will be summarised.

12.6 Secondary Analysis

12.6.1 Biodistribution

By using activity data from ROIs, data from the whole-body images, as well as activity data from serial blood and urine samples, descriptive statistics will be generated for biodistribution data (decay-corrected percentage administered activity per organ) at each time point for each organ and tissue of interest in HVs. Time-activity curves will then be generated from ^{123}I activity data from all 8 subjects and integrated to obtain the normalised-cumulated activity in each source region, which will be summarised with descriptive statistics. The amount of ^{123}I activity in plasma and excreted in urine will be calculated from the product of concentration of ^{123}I activity measured in each sample and the volume of each sample.

The cumulative amount of ^{123}I activity excreted in urine will be tabulated for each subject and summarised. In addition, the normalised cumulative activity in each source region will be compared between the Chinese subjects from this study and European subjects by using the 2-sample t-test.

SBR will be analysed to determine the stability of striatal uptake relative to a reference region over the proposed imaging window of 3 to 6 hours after administration. The difference

between the SBR at 3 and 6 hours calculated for each subject will be tested by Wilcoxon signed-rank test.

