| Safety and Biodistribution/Dosimetry Variables: 
Safety Variables:
 
Primary Outcome Measures:
 
Safety variables will include monitoring of the following:
 
 Occurrence of AEs up to study exit Results of a tolerability questionnaire to be completed at prespecified time points Results of physical examinations at prespecified time points Results of clinical laboratory tests at prespecified time points Results of injection site monitoring at prespecified time points Results of vital signs (blood pressure, heart rate, body temperature, respiratory rate) and oxygen saturation at prespecified time points Results of ECG examinations at prespecified time points 
Secondary Outcome Measures: Dosimetry estimates and cumulated activity by source region and by entire body (including whole blood, plasma, and excreted urine) at time points up to 48 hours after administration in HVs.
 
Biodistribution/Dosimetry:
 
Biodistribution data in HVs will consist of ¹²³I activity in organs and tissues of interest at multiple time points, ¹²³I activity in whole blood and plasma at multiple time points, and ¹²³I activity in voided urine. The ¹²³I activity in voided urine will be calculated as the product of the ¹²³I activity measured in each void multiplied by the volume of that void. The absorbed doses of radiation to organs and tissues will be evaluated for the Cristy-Eckerman female and hermaphrodite male phantoms. Descriptive statistics of absorbed doses to the target organs and tissues specified in the MIRD schema will be tabulated.
 
Imaging Variables:
 
Planar whole-body scanning will be performed serially at prespecified time points over a period of approximately 48 hours after administration (n=8 HVs). Brain SPECT imaging will be acquired at 3 and 6 hours after administration (n=8 HVs).
 
Statistical Methods and Planned Analysis:
 
Tabulations of summary statistics, graphical presentations, and statistical analyses will be performed with SAS® software. No confirmatory hypothesis testing is intended to be performed. P-values will be interpreted as a metric of uncertainty. All data will be listed by subject number and time point (if applicable). Confidence intervals, both individual and simultaneous, will be at the 95% confidence level unless otherwise noted. The last pre-administration observation will be used as the baseline value for calculating post-administration changes from baseline. Demographic and other baseline information will be summarised.
 
An overall summary of AEs will be presented, and they will be coded with Medical Dictionary for Regulatory Activities (MedDRA) and summarised by MedDRA system organ class and preferred term. Results of the following evaluations performed before and after DaTSCAN™ administration will be summarised with
 | | |

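### Section 12.6.1 calculates the amount of 123I in plasma from the sample's own volume, which gives the activity in the tube and not in the subject's plasma

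*Combined protocol and SAP*

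**What the plan says.** Section 12.6.1 defines both amounts in one sentence: "activity in plasma and excreted in urine will be calculated from the product of concentration of" the isotope and sample volume. Plasma and urine share this one definition, and the volume in it is that of the sample itself.

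Section 10.2.1.3 describes the samples. Each blood draw is up to 5 mL. An aliquot is taken for whole-blood counting, then "the remaining blood will be centrifuged to obtain plasma", and the CRF records the "number of counts per specified time interval in 0.5 mL plasma". For urine, every void to 48 hours is collected and its total volume is recorded.

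The secondary outcome in the Synopsis and Section 10.2 covers "cumulated activity by source region and by entire body (including whole blood, plasma, and excreted urine"), at times up to 48 hours. Section 12.6.1 expresses biodistribution as a percentage of administered activity, corrected for decay.

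Elsewhere the two fluids are treated differently. Section 10.2.1.2 speaks of "activity concentrations in whole blood and plasma and the rate and amount of" 123I activity excreted in urine, so plasma is a concentration there and only urine is an amount. The Synopsis and Section 10.2.1 apply a volume product to urine alone: "activity measured in each void multiplied by the volume of that void".

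**The concern.** Concentration times volume gives the amount in whatever that volume encloses. A void is the whole of what was excreted on that occasion, so its volume is the right multiplier. A plasma sample is a small fraction of a circulating compartment, so its volume is not. Followed as written, the rule labels the contents of a counting tube as the amount of 123I in plasma.

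Plasma is named in the cumulated-activity outcome. Any percentage of administered activity, or any cumulated plasma activity, built on this product would carry the same error. The right multiplier is the subject's own plasma volume, so no single constant applied to the finished table would repair it.

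Several quantities are not touched: plasma concentrations and their time course, clearance based on concentration, and curve shape or half-life when the aliquot is always 0.5 mL.

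**Working it through.** The plan states no plasma amount, plasma volume or scaling factor, so there is no figure of that kind to reproduce. The sample sizes can be checked against the stated blood total: 1 pre-dose and 10 post-dose draws of up to 5 mL give 11 × 5 = 55 mL, which matches the maximum in Section 10.2.1.3. No sample is therefore larger than 5 mL of blood.

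**Inputs**
- Plasma aliquot counted: 0.5 mL (Section 10.2.1.3).
- Blood draw: up to 5 mL (Section 10.2.1.3).
- Administered activity: 111 MBq nominal (Section 8.1.1).
- Circulating plasma volume: 2,000 to 4,000 mL. This is an assumption and is not in the document.
- For one of the sensitivity readings: haematocrit 0.40 and 0.5 mL of blood removed for whole-blood counting. Both are assumptions.

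**Formula.** With plasma concentration C, the true amount is C × V_plasma and the plan's amount is C × V_sample. The understatement factor is V_plasma / V_sample, whatever C is.

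**Results.** Section 12.6.1 does not say which volume counts as the sample, so three readings are shown.

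| Reading of sample volume | V_sample | Factor at 2 L | Factor at 4 L |
|---|---|---|---|
| Counted aliquot | 0.5 mL | 2,000/0.5 = 4,000 | 4,000/0.5 = 8,000 |
| All plasma recovered | (5 − 0.5) × (1 − 0.40) = 2.7 mL | 2,000/2.7 = 741 | 4,000/2.7 = 1,481 |
| Upper bound, the whole draw | 5 mL | 2,000/5 = 400 | 4,000/5 = 800 |

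The plasma in a draw must be less than the draw itself, so with at least 2 L of plasma the factor cannot fall below 400.

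**Illustration.** Suppose plasma truly holds 5% of the dose: 0.05 × 111 MBq = 5.55 MBq.
- With 2 L of plasma: 5,550 kBq / 2,000 mL = 2.775 kBq/mL. Times 0.5 mL is 1.39 kBq, and 1.39/111,000 = 0.00125% of the dose.
- With 4 L of plasma: 5,550 kBq / 4,000 mL = 1.3875 kBq/mL. Times 0.5 mL is 0.69 kBq, or 0.00063% of the dose.

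Both should read 5%. Equal true amounts also come out 2-fold apart, because the rule ignores plasma volume. The two volumes are the ends of the assumed range; the spread among the 8 subjects is unknown.

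**Summing over samples does not help.** The 10 post-dose aliquots total 10 × 0.5 = 5 mL, which is 5/4,000 = 0.125% to 5/2,000 = 0.25% of the plasma volume.

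**The case against.** The strongest reply is that this is loose drafting with little consequence. Section 10.2.1.2 treats plasma as a concentration and urine as an amount, and the only cumulative amount that Section 12.6.1 goes on to tabulate is urinary. No section says that the plasma product feeds the cumulated-activity outcome. Organ source regions come from images, and the European t-tests concern source-region cumulated activity, absorbed doses and effective dose. The largest factors depend on the 0.5 mL reading, and every factor depends on an assumed plasma volume. A plasma total near 0.001% of the dose would look implausible to anyone reporting it. Sampling time, counting time and counts are on file, so it could be recalculated. A scaling step might also sit in the sponsor's dosimetry SOP or in the Imaging Manual.

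Much of this stands, and it limits the consequence. No effect is shown on organ doses, effective dose or the European comparisons, and the error is recoverable. It does not make the rule right. Section 12.6.1 commits to a plasma amount and defines it wrongly under every reading of sample volume. Section 10.2.5 defers to the SOP only where the protocol does not specify otherwise, and here it does specify. Section 10.2.1.3 cites the Imaging Manual for collection procedures and assay times, not for this calculation. An analyst who quietly corrected the formula would be departing from the stated analysis, which Section 12.12 requires to be reported with reasons.

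**Conclusion.** The concern holds. As written, Section 12.6.1 returns the 123I activity in the plasma sample and calls it the amount in plasma, and the document contains no step that scales it to the subject. Under an assumed plasma volume of 2 to 4 L, the understatement is 4,000- to 8,000-fold for the 0.5 mL aliquot, the only plasma volume the document names, and at least 400-fold on any reading. Only the size depends on that assumption; the direction and nature of the error do not.

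The damage is confined to the plasma amount and anything derived from it. It warrants correction before analysis, but it does not threaten the safety objective.

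The urine point is one of wording only. The Synopsis and Section 10.2.1 say activity times volume where Section 12.6.1 says concentration times volume. The recorded urine data are enough to scale correctly, so no wrong urine result is claimed.

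**What to change.** In Section 12.6.1, restrict the product to urine: activity concentration in the void times the volume of the void. Report plasma as decay-corrected percentage of administered activity per mL. Where a total or cumulated plasma activity is needed, multiply the concentration by a subject-specific plasma volume predicted by a named, prespecified formula from sex, height and weight, with haematocrit if the formula uses it. In the same edit, change the urine wording in the Synopsis and Section 10.2.1 to activity concentration. The outcome also names whole blood, for which Section 12.6.1 gives no amount rule, so it would be sensible to state how that is reported at the same time.

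The cost is one rewritten sentence and two wording changes. No new data are needed: "Demographic data (age/date of birth, weight, height, BMI, sex and race) will be collected during the screening visit" (Section 10.3), and haematocrit is in the laboratory panel (Section 10.1.1, Table 2). The one drawback is that any plasma total will then rest on a predicted volume, not a measured one, and the report should say so.

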
| | | |
|---|---|--|
| Name of Sponsor/Company: GE Healthcare Ltd. and its Affiliates | Individual Study Table Referring to Part of Dossier in Which the Individual Study or Study Table is Presented: | (For National Authority Use Only) |
| Name of Finished Product: DaTSCAN™ | | |
| Name of Active Ingredient: Ioflupane (¹²³ I) | Volume: Reference: | |
| observed values and changes from baseline: physical examinations, 12-lead ECGs, vital signs (blood pressure, heart rate, respiratory rate, and body temperature) and oxygen saturation, injection site monitoring, and clinical laboratory evaluations (haematology, serum biochemistry, and urinalysis). Concomitant medications will be summarised. In addition, results of the tolerability questionnaire given after DaTSCAN™ administration will be summarised in descriptive statistics and boxplot. Dosimetry estimates (using MIRD methods) and cumulated activity by source region and by entire body (including whole blood, plasma, and excreted urine) at time points up to 48 hours after administration will be summarised. The ED as calculated by using International Commission on Radiological Protection (ICRP) methods will be summarised. In addition, the following measures will be compared between the Chinese subjects from this study and European subjects: the normalised cumulative activity, absorbed doses, and ED. These measures will be compared by using the 2-sample t-test. Striatal binding ratios (SBR) will be analysed to determine the stability of striatal uptake relative to a reference region over the proposed imaging window of 3 to 6 hours after administration. The difference between the SBR at 3 and 6 hours calculated for each subject will be tested by Wilcoxon signed-rank test. | | |
| Sample Size Estimates: No sample size calculations were performed. The sample size has been chosen to fulfil local regulatory requirements. | | |

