12.6.4 Statistical Hypothesis, Model, and Method of Analysis

No confirmatory hypothesis testing is intended to be performed in this study.

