12.6.5 Handling of Missing Values/Censoring/Discontinuations

Missing values will not be substituted by estimated values but treated as missing in the statistical evaluation. All data from all subjects dosed in the study will be included in all listings, plots, summary tables, and statistical analyses when appropriate.

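### The 3-to-6-hour SBR stability question has a signed-rank test of no change as its only named analysis; no confidence interval for the change is committed (minor).

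*Combined protocol and SAP*

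**What the plan says.** The purpose is stated in the synopsis and again in section 12.6.1: "Striatal binding ratios (SBR) will be analysed to determine the stability of striatal uptake relative to a reference region over the proposed imaging window", the window being 3 to 6 hours after administration. In both places the next sentence names the method, which is that the difference "between the SBR at 3 and 6 hours calculated for each subject will be tested by Wilcoxon signed-rank test". Nothing further is specified for SBR: no estimate, no interval, no margin and no rule for reading the result. Section 10.2.2 says that left and right SBR are both determined at each time. Section 12.6.1 does not say whether the tested difference is left, right or an average.

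Several general rules bear on this:
- Section 12.1: "Descriptive statistics for continuous data in summary tables will include the number of subjects in the analysis (n), mean, standard deviation, median, and range". The list contains no confidence interval.
- Synopsis, repeated in section 12.5: "Confidence intervals, both individual and simultaneous, will be at the 95% confidence level unless otherwise noted". This fixes the level of any interval produced but does not commit one for SBR.
- Synopsis: "P-values will be interpreted as a metric of uncertainty".
- Section 12.6.4: "No confirmatory hypothesis testing is intended to be performed in this study".
- Section 12.6.5: "All data from all subjects dosed in the study will be included in all listings, plots, summary tables, and statistical analyses when appropriate".

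Sections 12.8 and 12.9 say that no sample size or power calculation was made. Section 12.6.6 plans no sensitivity analysis.

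**The concern.** Stability is a question about size: how far could SBR have moved between the two scans and still be compatible with these data? A signed-rank test has no change as its null hypothesis, and its p-value mixes the size of the drift with its consistency and the number of pairs. A large p-value can accompany a substantial drift, and a small one can accompany a trivial drift. If the report follows the SBR text alone, the one named result for the stability question will not answer it.

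As background only, the summary of amendment A01 links the 3- and 6-hour SPECT results to label wording for that imaging window. The result is therefore meant to be used, but this does not raise the weight of the point.

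**Working it through.** **Inputs.** Eight evaluable subjects (section 6.1) and a Wilcoxon signed-rank test on the per-subject difference (section 12.6.1). The plan gives no SD, margin, alpha or power for SBR, so there is no figure of its own to reproduce. A two-sided 0.05 cut-off and normally distributed differences are assumptions made here for illustration.

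**1. Exact null distribution, n = 8.** There are 2^8 = 256 equally likely sign patterns. With T the smaller rank sum:
- All signs alike: two-sided p = 2/256 = 0.0078, the smallest possible value.
- T ≤ 3: 2 × 5/256 = 0.0391.
- T ≤ 4: 2 × 7/256 = 0.0547.

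A 0.05 reading therefore rejects at T ≤ 3, an actual level of 3.9%.

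**2. Chance of a non-significant result** (simulation, normal differences, reject at T ≤ 3):

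| True drift, in SDs of the within-subject change | Non-significant |
|---|---|
| 0.5 | 81% |
| 1.0 | 39% |
| 1.5 | 8% |

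**3. What the p-value hides.** Three invented sets of eight percentage changes:

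| Set | Values (%) | Mean | SD | Exact p | 95% t interval |
|---|---|---|---|---|---|
| A | 0.6, 0.7, 0.8, 0.9, 1.1, 1.2, 1.3, 1.4 | 1.0 | 0.293 | 0.0078 | 0.8 to 1.2 |
| B | 10 × set A | 10.0 | 2.93 | 0.0078 | 7.6 to 12.4 |
| C | −13, −7, 2, 9, 15, 19, 24, 31 | 10.0 | 15.24 | 0.109 | −2.7 to 22.7 |

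In set C the negative values carry ranks 2 and 4, so T = 6 and p = 2 × 14/256 = 0.109. A and B differ tenfold in size and share a p-value. B and C share a mean and differ in p-value. The interval separates all three.

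**4. What an interval would deliver at n = 8.** Half-width = t(0.975, 7)/√8 × SD = 2.365/2.828 × SD = 0.836 × the observed SD. The documents give no SD, so a range is assumed, as a percentage of the 3-hour value:

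| Assumed SD of change | Half-width (percentage points) |
|---|---|
| 5% | 4.2 |
| 10% | 8.4 |
| 15% | 12.5 |
| 20% | 16.7 |

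The rank-based alternative is the Hodges-Lehmann estimate, with limits at the 4th smallest and 4th largest of the 8 × 9/2 = 36 Walsh averages. Its exact coverage is 1 − 0.0391 = 96.1%. For set C it gives 9.75, with limits −5.5 and 24.0.

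**5. Which pairs.** Two sides per subject make 16 side-level pairs for eight subjects, so the per-subject difference is undefined until a side or an average is named. The number of pairs is also not fixed. Withdrawn or incomplete subjects are or may be replaced (sections 7.4.1 and 12.2), while data from all dosed subjects are kept where appropriate (section 12.6.5). A subject with both SPECT scans but an incomplete blood series could be replaced and still supply an SBR pair. A missed scan would remove one.

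**The case against.** The strongest reply is that the plan has no decision rule for this test. It declares testing non-confirmatory and treats p-values as a measure of uncertainty, so a missed drift presupposes a cut-off the plan never sets. That is right. The percentages in step 2 are illustrations under added assumptions, not properties of the plan.

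Second, much of the content may already be covered. Values are listed by subject and time point, and the general summaries include mean and SD, from which a reader could compute a t interval. The general sentence on 95% intervals also suggests that some intervals will be produced. This stands and reduces the weight. What remains is that no text commits an interval for the SBR change.

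Third, sets A and B have SDs well below the assumed 5% to 20%. With a true drift of 1%, an SD of 5% and normal changes, the chance that all eight move the same way is about 0.579^8 + 0.421^8 = 1.4%. A trivial drift reaching p = 0.0078 would then be rare. The sets show what the p-value cannot distinguish, not what is likely.

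A reader might go further and infer that the sponsor will take non-significance as proof of stability, or that eight subjects are too few. The documents support neither. They nowhere say how the p-value will be turned into a stability statement, and they claim no power for secondary variables. The number of subjects is attributed to local regulatory requirements.

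**Conclusion.** The point holds as a minor one. The stated aim is to determine stability, and the only analysis named for it tests for no change without bounding the change. This follows from the text and needs no assumption. The illustrative sizes (39% non-significant at a drift of 1 SD; p = 0.0078 for any same-direction change in all eight) rest on eight pairs. The first also needs a two-sided 0.05 reading and normal differences. The half-widths in percentage points rest on assumed SDs. The weight is limited by the secondary, non-confirmatory status of the analysis and by the general summaries and listings, which may already supply part of what is needed.

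**What to change.** In the synopsis and section 12.6.1:

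- Make the main SBR result the within-subject change, 6 hours minus 3 hours, in absolute units and as a percentage of the 3-hour value, with a 95% confidence interval.
- Name one SBR variable per subject in advance, for example the mean of left and right, and show each side as well.
- Use however many complete pairs are available, and report that number.
- State one interval method beforehand: either the t interval for the mean, or the Hodges-Lehmann estimate with the exact interval that matches the Wilcoxon test. If the latter, report the attained coverage, which depends on the number of pairs (96.1% at n = 8; 1 − 6/128 = 95.3% at n = 7).
- Keep the Wilcoxon p-value as descriptive, and say that no stability statement will be based on non-significance.

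A formal equivalence margin is optional. None can be derived from the documents, so the sponsor would have to justify one.

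The cost is a few lines of wording in two places, with no additional scans or subjects. The drawback is that the interval may be wide, about ±17 percentage points at an assumed SD of 20%. The report may then have to say that stability is not established.
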